1.3 Other Objectives

- a. To explore the molecular variability in MM cells obtained from extramedullary bone marrow relapse sites.
- b. To explore the role of PET scanning in assessing disease burden and as a tool to assess treatment response.
- c. To explore changes in Left Ventricular Ejection Fraction (LVEF) in patients with relapsed or refractory multiple myeloma treated with low dose carfilzomib or high dose carfilzomib plus dexamethasone.
- d. To evaluate whether there is a difference in the incidence of clinically relevant cardiovascular toxicity between treatment arms (normal- versus high-dose carfilzomib).
- e. To assess the timing and onset of clinically significant cardiotoxicity.
- f. To assess the relationship between patient characteristics, including demographic data, comorbid conditions, clinical data, echocardiography, and serum biomarkers and the development of clinically significant cardiotoxicity.

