7.1 General Considerations

- a. Patients must have creatine kinase (CK), cardiac-specific troponin T (TnT) and/or troponin I (TnI) testing—both TnT and TnI preferred if available, creatine kinase-MB (CK-MB), brain natriuretic peptide (BNP) and/or proBNP performed on Cycle 1, Day 1. See [Section 9.0](#) for additional timepoints. In the event that Cycle 1, Day 1 laboratory tests are resulted and the patient no longer meets one or more of the eligibility criteria, treatment must be held. Laboratory tests and any associated supportive care must be repeated. If the repeat lab results fall within the eligibility criteria, treatment may be resumed. In the event that treatment must be held for \geq 28 days, the patient must be removed from the protocol.
- b. Patients on Arm 1 will receive dexamethasone/low-dose carfilzomib for up to 12 cycles or until progression that occurs after the start of Cycle 2, whichever comes first. If patient progresses after the start of Cycle 2 and prior to completion of 12 cycles, the patient will cross-over and be registered to Arm 3 where they may receive up to an additional 12 cycles of treatment.
- c. Results of Day 1 laboratory tests are not required prior to starting treatment for each cycle subsequent Cycle 1 (see Section 7.1a for instructions regarding D1, C1 results). If lab results are abnormal or indicative of adverse events, the treating physician should refer to Section 8.0 for dose modifications, and Response Assessments should be conducted at time of dose modification and as indicated in [Section 9.0](#). If dose modification is not indicated, the physician should otherwise continue treatment at physician discretion.
- d. Patients on Arm 2 will receive dexamethasone/high dose carfilzomib for up to 12 cycles, or until progression that occurs after the start of Cycle 2, whichever comes first. If a patient progresses after the start of Cycle 2, the patient will discontinue protocol treatment.

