7.4 Registration Step – Crossover Registration (Arm 3)

Note that patients who cross over from Arm 1 to Arm 3 must be registered to Step 2 prior to initiation of cross-over treatment on Arm 3.

Agent	Dose	Route	Day	Schedule*
Dexamethasone ^b	20 mg	IV	1, 2, 8, 9, 15, 16	up to 12 cycles
Carfilzomib ^a	56 mg/m ²	IV over 30 mins	1, 2, 8, 9, 15, 16	Cycles 1-12

* Note: 1 cycle = 28 days

^a For Arm 3, Cycle 1 carfilzomib dosing is not reduced, but given at the full 56 mg/m² (see Section 7.3a for dose capping based on BSA).

^b On all treatment days, dexamethasone will be administered 30 minutes prior to the carfilzomib infusion.

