7.5 Supportive Care and Concomitant Medication

a. Antiviral Prophylaxis

All patients should receive antiviral prophylaxis with acyclovir 400 mg orally two times daily (or an equivalent regimen as per institutional guidelines) while they are on study treatment. It is recommended that patients continue antiviral prophylaxis for at least 8 weeks after discontinuing treatment.

b. Pneumocystis Pneumonia (PCP) Prophylaxis

The probability of PCP should be considered based on previous treatments received and prophylaxis should be administered per local institutional guidelines at the discretion of the treating physician,

c. Concomitant Medication

Any systemic, anti-myeloma therapy or steroids other than those prescribed by the protocol are prohibited while on protocol therapy. Guidelines for selection and use of other concomitant medications should be derived from the carfilzomib and dexamethasone prescribing information. Other than study medications, administration of any therapeutic or diagnostic investigational agent (for any indication) is prohibited while on study.

d. G-CSF

G-CSF use is allowed in accordance with ASCO guidelines.

e. Bisphosphonates

Bisphosphonate use is allowed per local institutional guidelines at the discretion of the treating investigator.

f. Radiation Therapy

Radiation therapy is allowed per local institutional guidelines at the discretion of the treating investigator ONLY for localized disease symptom control.

g. Additional Monitoring

All patients will undergo EKG, ECHO and cardiac blood marker testing every 12 weeks while on study.

All patients that have evidence of extramedullary progression (EMP) will have a follow-up PET scan at the end of treatment or at the time of achieving VGPR or better, whichever occurs earlier (see Section [15.1](#)).

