11.5 Analysis of Secondary Endpoints

Secondary efficacy endpoints include response rate (PR or better) and overall survival (OS). All efficacy analyses will be performed on intent to treat basis. The response rate (sCR, CR, VGPR, PR) for each arm will be determined by the number of patients achieving a response as defined in Section [10.3](#) divided by the number of patients assessed for response in each arm and compared between arms using Fisher's exact test.

The response rate for patients who relapse on Arm 1 and cross-over to Arm 3 will also be determined in order to determine whether response can be re-captured for those patients by increasing the carfilzomib dose.

Overall survival will be assessed in each arm using the method of Kaplan Meier and compared using the stratified log-rank test.

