In order to evaluate whether there is a difference in the incidence of clinically relevant cardiovascular toxicity, between treatment arms (normal- versus high-dose carfilzomib), where a clinically relevant cardiovascular toxicity is defined as the clinical development of any of the following toxicities per Common Terminology Criteria for Adverse Events version 4.0 (CTCAE v4.0) of Grade 2 or higher: congestive heart failure, dyspnea, edema, or arrhythmia, a decrement in left ventricular ejection fraction on echocardiogram $> 10\%$ from baseline (per central review) or to less than 53% absolute, or an increase in global longitudinal strain (GLS) by $> 15\%$ from baseline (per central review), the proportion of patients experiencing cardiovascular toxicity at any time while on study will be compared between the two treatment arms. [\(33\)](#) Assuming a clinically relevant cardiovascular toxicity rate of 8% in the control arm, a binomial test with a one-sided significance level of 0.1 and 63 eligible patients in each arm has 79% power to detect a difference of 15% between arms. Furthermore, a multivariate Cox Proportional Hazards model estimating time-to-clinically significant cardiovascular toxicity will be developed using a stepwise selection procedure and will consider potentially relevant baseline factors including patient demographic data, comorbid conditions, clinical data, echocardiography and serum biomarkers, where a clinically significant cardiotoxicity is defined as Grade 2 or greater cardiac toxicity per CTCAE v4.0, following subclinical myocardial dysfunction, as defined by abnormalities in LV strain (an increase of GLS $> 15\%$) and/or in serum biomarker levels (NTproBNP, BNP, CKMB, Troponin T, or Troponin I levels that are greater than the upper limit of normal from the reference range of the testing laboratory). All patients who are eligible and who have been assessed for toxicity will be included in the above described analyses. Additionally, the timing and onset of clinically significant cardiotoxicity from the onset of the earliest occurrence of subclinical myocardial dysfunction will be evaluated using cumulative incidence analysis. All patients who are eligible, who have been assessed for toxicity, and who have developed a subclinical abnormality will be included in this analysis.

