15.2 Translational Medicine and Banking (optional for patient)

Specimens for translational medicine and banking (submitted to the SWOG Specimen Repository – Solid Tissue, Myeloma and Lymphoma Division, Lab #201):

- a. With patient's consent bone marrow biopsy core specimens must be submitted at the following times (see Section [9.0](#)):
 1. Pretreatment (within 28 days prior to Step 1 registration)
 2. Progression (including second progression for patients who cross over to Arm 3)

- b. With patient's consent serum and bone marrow aspirate specimens must be submitted at the following times (see Section [9.0](#)):
 - 1. Pretreatment (within 28 days prior to Step 1 registration)
 - 2. Progression (including second progression for patients who cross over to Arm 3)
- c. Note that in addition to regular aspirate and biopsy core submission, submission of aspirate/core from extramedullary disease site is also required with patient consent.

If extramedullary site specimen is an aspiration, process as if the sample were a bone marrow aspiration. If this is a biopsy, process the sample as if it were a core biopsy of the iliac crest.
- d. Specimen collection and submission instructions can be accessed on the SWOG Specimen Submission webpage, (<http://swog.org/Members/ClinicalTrials/Specimens/MyelSpecimens.asp>).
- e. Specimen collection kits are not being provided for this submission; sites will use institutional supplies.

15.3: ECHO Imaging (mandatory)

A standard echocardiogram will be obtained for all patients at 28 days prior to registration, then after completion of treatment on Cycles 3, 6, 9, and 12, and at time of completion of treatment for any reason (unless echocardiogram had been performed within the previous 28 days). For patients who cross over to Arm 3, ECHOs will be performed every 3 cycles, based on the date of previous measurement.

The development of significant cardiotoxicity by echocardiography is defined as a decrease in the LVEF of > 10 percentage points, to a value < 53% (normal reference value for 2 dimensional echocardiography (2DE) or >15% increase in global longitudinal strain (GLS) from baseline.

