Images will be submitted for central review at Oregon Health and Science University via AG Mednet (as outlined in [Appendix 18.2](#)). De-identified echocardiograms will be copied to CD in standard DICOM format and mailed to the coordinating site for further analysis. Each echocardiogram will undergo 2D speckle-tracking deformation imaging using EcholnSight®, a vendor-independent analysis package. Apical 4-, 3-, and 2-chamber views will be traced manually for calculation of segmental strain and GLS of the left ventricle (LV). The apical view of the right ventricle (RV) will similarly be analyzed for assessment of RV free-wall strain. The parasternal short axis view at the level of the papillary muscles will be analyzed for circumferential and radial strain. Subsequent to strain analysis, each echocardiogram will undergo further analysis for standard 2DE calculation of volumetric LV ejection fraction (LVEF) using the Simpson's biplane method of discs. Right ventricular function will be further quantified using RV fractional area change (FAC), tricuspid annular plane excursion (TAPSE), and RV S' velocity.

ECHO Images will also be subsequently compared to mandatory cardiac monitoring test results, including: EKG, CK, CK-MB, BNP and/or pro-BNP as well as troponin testing that were submitted in accordance with Sections 7.5g and 9.0 at 6 time points for EKG, ECHO, CK, CK-MB, BNP and/or NTpro- BNP (10 in the event of crossover to Arm 3) and 5 time points for troponin testing (9 in the event of crossover to Arm 3).

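### Section 11.6 compares cardiovascular toxicity by dose with no cut at crossover, so read as written Arm 3 events at 56 mg/m² count in low-dose Arm 1

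*Combined protocol and SAP*

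**What the plan says.** **The comparison.** Objective 1.3d is "To evaluate whether there is a difference in the incidence of clinically relevant cardiovascular toxicity between treatment arms (normal- versus high-dose carfilzomib"). Section 11.6 carries it out by comparing the proportion of patients "experiencing cardiovascular toxicity at any time while on study will be compared between the two treatment arms". It includes all eligible patients assessed for toxicity. It states 79% power for a 15-point difference from 8%, with 63 patients per arm and a one-sided level of 0.1.

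**Crossover.** Under Section 7.1b, if an Arm 1 patient progresses after the start of Cycle 2 and before completing 12 cycles, "the patient will cross-over and be registered to Arm 3 where they may receive up to an additional 12 cycles of treatment". Section 7.4 sets Arm 3 at 56 mg/m² and adds: "For Arm 3, Cycle 1 carfilzomib dosing is not reduced".

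**Cardiac testing after crossover.** Section 7.5g: "All patients will undergo EKG, ECHO and cardiac blood marker testing every 12 weeks while on study". Section 15.3: "For patients who cross over to Arm 3, ECHOs will be performed every 3 cycles, based on the date of previous measurement". Section 15.3 also counts the tests done under Sections 7.5g and 9.0 as 6 time points for ECHO, EKG and most markers, or "10 in the event of crossover to Arm 3".

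**Arm 3 in other analyses.** Section 11.5 treats Arm 3 separately for response: "The response rate for patients who relapse on Arm 1 and cross-over to Arm 3 will also be determined". Section 11.6 has no counterpart for toxicity.

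**LVEF criterion.** Section 11.6 counts a fall of more than 10% from baseline, or a fall to below 53%. Section 15.3 reads as a fall of more than 10 percentage points that also ends below 53%.

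**The concern.** The question is about dose, but the counting window follows the patient through a change of dose. An Arm 1 patient whose first cardiac event occurs on 56 mg/m² in Arm 3 is, on the plan's wording, an Arm 1 event. Such a patient also has up to 10 − 6 = 4 further scheduled ECHOs, taken on the high dose, in which an LVEF or strain event can be found.

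Compared with stopping at crossover, adding these events can only raise the Arm 1 proportion. If the high dose carries more cardiac risk, the two arms move together and an excess may be missed. This is the plan's only stated dose comparison for cardiac toxicity over the whole study.

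A separate wording problem affects the same endpoint: a given pair of LVEF readings can be an event under Section 11.6 and not under the LVEF wording of Section 15.3.

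**Working it through.** **1. The plan's own power figure.** Inputs from Section 11.6: p1 = 0.08, p2 = 0.23, n = 63 per arm, one-sided α = 0.10 (z = 1.2816).

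- Normal approximation with continuity correction: Φ[(0.15 − 1/63 − 1.2816 × SE0)/SE1], where SE0 = √(2 × 0.155 × 0.845/63) = 0.0645 and SE1 = √((0.08 × 0.92 + 0.23 × 0.77)/63) = 0.0631. Result: 0.793.
- Exact power of Fisher's test: 0.800.

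The stated 79% is reproduced for an uncontaminated contrast. This takes the 8% to be a low-dose rate before crossover, which the text does not say.

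**2. How many could cross over.** Section 11.2 gives a 9-month median PFS in Arm 1 and assumes exponential progression times. Cycles last 28 days, so Cycle 2 starts at 0.92 months and Cycle 12 ends at 11.04 months.

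exp(−ln2/9 × 0.92) − exp(−ln2/9 × 11.04) = 0.50

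This is a ceiling, because PFS events include deaths and because refusals and the Section 5.2 exclusions reduce it.

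**3. Effect of counting Arm 3 events in Arm 1.** Let f be the share of Arm 1 that crosses over and e the added risk per crossover patient. Neither is in the documents. Arm 1 rate = 0.08 + f × e; Arm 2 stays at 0.23. Exact Fisher power:

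| e | f = 0.2 | f = 0.3 | f = 0.4 | f = 0.5 |
|---|---|---|---|---|
| 0.075 | 0.71 | 0.66 | 0.61 | 0.56 |
| 0.10 | 0.68 | 0.61 | 0.55 | 0.48 |
| 0.15 | 0.61 | 0.51 | 0.42 | 0.33 |

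The Arm 1 rate runs from 0.08 + 0.2 × 0.075 = 9.5% to 0.08 + 0.5 × 0.15 = 15.5%. The middle case is 0.08 + 0.3 × 0.10 = 11.0%, power 0.61.

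**4. What a cut at crossover does to exposure.** Mean progression-free time within 12 cycles is (1 − exp(−λ × 11.04))/λ, with λ = ln2/median. This gives 7.44 months in Arm 1 (median 9) and 8.65 in Arm 2 (median 15). Raw proportions after the cut are therefore not comparable. With a constant toxicity hazard h and competing progression rate λ, P = h/(h + λ) × (1 − exp(−(h + λ) × 11.04)). At equal hazards:

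- 8.0% in Arm 1 corresponds to 9.3% in Arm 2. One-sided Fisher rejection is 0.08, against 0.05 if the rates were equal.
- 20% in Arm 1 corresponds to 23% in Arm 2. Rejection is 0.14, against 0.07.

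A log-rank test censored at progression or 12 cycles (20,000 simulated trials, no 30-day tail) rejects in 0.11 and 0.10 of those two null cases, against a nominal 0.10. For 8% versus 23% (h = 0.01135 and 0.03095 per month) its power is 0.79.

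**5. The LVEF wording on examples.**

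| LVEF change | Section 11.6 | Section 15.3, LVEF wording |
|---|---|---|
| 65% to 54% | event (fall over 10%) | no (not below 53%) |
| 57% to 52% | event (below 53%) | no (fall of 5 points) |
| 50% to 48% | event (below 53%) | no (fall of 2 points) |
| 65% to 58% | event only if 10% is relative (7/65 = 10.8%) | no |

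The third row can occur because Section 5.1m admits patients with an ejection fraction of 45% or more.

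**The case against.** **The reading is inferred.** No sentence assigns Arm 3 events to Arm 1. Arm 3 has its own name and registration step, and the normal- versus high-dose label could be taken to mean events on the assigned dose. Section 7.5g is a monitoring instruction, and the time-point count in Section 15.3 describes comparing ECHOs with other cardiac tests. That is fair as far as it goes. But Section 11.6 does state a window, the protocol's use of on-study monitoring covers Arm 3, and no rule puts the dose label into effect. Intent-to-treat is declared only for efficacy (Sections 11.3 and 11.5), so the window cannot be read as a declared intent-to-treat choice for toxicity.

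**A dose gradient is not established.** Section 2.0 cites Grade 3 or higher cardiac failure in 6% of 526 patients in the lower-dose studies, and heart failure of that grade in 6% of 65 at 20/56 mg/m². These small cross-study figures do not exclude a gradient, but the bias toward no difference is conditional on one. Without a gradient, the extra Arm 3 observation would still raise Arm 1, and would then make the low dose look worse.

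**The size is assumed.** This stands. Section 5.2f also bars crossover after an ejection fraction fall of more than 10%, or a fall with signs of NYHA Class III or IV heart failure. Crossover patients are therefore selected for preserved cardiac function, which makes the full 15-point excess an extreme.

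**The remedy has its own costs, and the analysis is exploratory.** An any-time comparison by assigned arm is a legitimate quantity, and cutting at crossover makes exposure unequal. Both are true; the first supports keeping that analysis as a sensitivity analysis, and the second is why a censored comparison is needed. Section 11.6 itself calls these analyses hypothesis-building, which limits the severity. The LVEF conflict is a separate matter of definition and does not support the crossover point.

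**Conclusion.** The concern holds. The stated window, followed as written, mixes doses in Arm 1 for a comparison framed by dose, and nothing elsewhere in the protocol corrects it. Confidence is high that the rule is missing.

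The size is uncertain. Power falls from 0.80 to 0.71–0.33 over the assumed range. The 0.33 needs both the 50% crossover ceiling and the full 15-point excess, and the middle case is 0.61. The claim of bias toward no difference rests on cardiac risk rising with dose.

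The primary endpoint is untouched, and the plan's 79% is correct for the contrast it describes. The change should be made, but it is not critical to the trial's main conclusion. The LVEF definitions in Sections 11.6 and 15.3 do conflict and need to be reconciled.

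**What to change.** **Change to make**

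1. For the arm comparison in Section 11.6, count events from first dose to the earlier of Step 2 registration or 30 days after the last Arm 1 or Arm 2 dose. Report Arm 3 events separately.
2. Compare time to first event, censored at that cut, by log-rank test with cumulative incidence curves, or give events per patient-month on the assigned dose. Do not rely on raw proportions alone.
3. Keep the any-time comparison by assigned arm as a labelled sensitivity analysis.
4. Apply the same split to the arm-level toxicity tables under Section 11.8.
5. Write one LVEF definition for analysis: OR or AND, relative or absolute change, and how patients entering at 45–52% are scored.

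**Cost**

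Wording and programming only. Section 14.4 already collects the Step 2 form, treatment and adverse event forms, cardiac assessments and ECHO images. Footnote 9 of the study calendar requires an ECHO at completion of treatment unless one was done in the previous 28 days, so a closing value exists before the cut, though it may be up to 28 days old. A memorandum at the front of the protocol already promises a revision to Section 11.8, and this could join it.

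**Downsides to state in the plan**

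- Arm 1 exposure is shorter (7.4 versus 8.6 months in the working above).
- Censoring at progression assumes that cardiac risk is unrelated to progression.
- Section 5.2b puts Step 2 registration 14 to 28 days after the last Arm 1 treatment, so crossover patients lose 30 − 28 = 2 to 30 − 14 = 16 days of the 30-day window.

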Currently there is evidence supporting the fact that recently developed echocardiographic indices and biomarkers may be useful in the detection of early cardiac injury; In particular abnormalities in myocardial strain and strain rate have been described after anthracyclines-based chemotherapies. (23-26)

Proteasome inhibitors are commonly used novel therapeutic agents for multiple myeloma and other B cell malignancies. The ubiquitin proteasome pathway is essential for many cellular regulatory mechanisms, including antigen processing, signal transduction, and cellular homeostasis. Proteasome inhibition results in proteotoxic stress. This may impair the ability of the cell to proliferate and can result in programmed cell death via activation of apoptotic pathways.

In the case of bortezomib, cardiovascular safety pharmacology studies conducted in primates show that the administration of dosages $\geq 3.0 \text{ mg/m}^2$ resulted initially in physiologically significant heart rate elevations, progressive hypotension, bradycardia, and death 12–14 h post-dose. Additional cardiovascular effects have been noted at even lower doses (1.2 – 2.4 mg/m^2). Furthermore, radioactively labeled bortezomib has been detected in the myocardium and histopathological findings in repeat-dose primate studies have showed cardiac necrosis at commonly used therapeutic doses ($\geq 0.9 \text{ mg/m}^2$). Whether these findings are associated with direct drug-myocardial toxicity is unknown, but it has been proposed this may occur through direct proteasome inhibition (the ubiquitin–proteasome system). (27-29)

In the pivotal clinical trial, of the 669 multiple myeloma patients who were treated with bortezomib, the incidence of cardiac disorders during treatment was 15% and clinical heart failure events occurred in 5% of bortezomib-treated patients. (30)

Carfilzomib is a newer irreversible proteasome inhibitor. It has shown good response rates in newly diagnosed and relapsed patients with multiple myeloma in a number of Phase I and II trials. Currently carfilzomib has less clinical data regarding cardiotoxicity than bortezomib, however, there are now over 500 patients with multiple myeloma that have been treated with carfilzomib in Phase II studies, including the AO-003 (20 mg/m^2), A1-003 (20/27 mg/m^2), 004 (20 and 20/27 mg/m^2) and the 005 (15/20 and 27 mg/m^2). The cardiac and pulmonary safety profile of carfilzomib in these 4 studies revealed:

	N= 526	%
Grade ≥ 3 arrhythmia	12	2%

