Grade ≥ 3 cardiac failure	30	6%
Grade ≥ 3 Cardiomyopathy	3	<1%
Grade ≥ 3 ischemic heart disease	7	1%
Dose reduction due to cardiac AE	6	1%
Discontinuation due to Cardiac AE	23	4%
Cardiac Deaths	5	1%
All grades dyspnea	222	42%
All grades cough	137	26%
(31)		

Carfilzomib at higher doses of 20/ 56 mg/m^2 (trials 007 and the IST- CAR 512) in 65 patients resulted in \geq Grade 3 heart failure in 6% and pulmonary edema in 5%. (32)

Inclusion of Women and Minorities

This study was designed to include women and minorities, but was not designed to measure differences of intervention effects. The anticipated accrual in the ethnicity/race and sex categories is shown in the table below.

Ethnic Category	Females	Males	Total
Hispanic or Latino	5	9	14
Not Hispanic or Latino	56	70	126
Total Ethnic	61	79	140
Racial Category			
American Indian or Alaskan Native	0	1	1
Asian	1	2	3
Black or African American	9	11	20
Native Hawaiian or other Pacific Islander	0	1	1
White	51	64	115
Racial Category: Total of all Subjects	61	79	140

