1. The following adverse events have been observed in early phase trials with possible relationship to carfilzomib and summarized from the investigator's brochure.

Adverse Events with Possible Relationship to Carfilzomib		
Likely (>20%)	Less Likely (4 - \leq 20%)	Rare but Serious (\leq 3%)
BLOOD AND LYMPHATIC SYSTEM DISORDERS		
Anemia	Leukopenia	Thrombotic Thrombocytopenic Purpura/Hemolytic Uremic Syndrome (TTP/HUS)
Neutropenia	Lymphopenia	Thrombotic Microangiopathy
Thrombocytopenia		
CARDIAC DISORDERS		
	Hypertension	Acute coronary syndrome
	Hypotension	Cardiac arrest
	Congestive heart failure	Cardiac disorder
		Decreased ejection fraction
		Hypertensive crisis
		Pericardial Effusion
		Pericarditis
EYE DISORDERS		
	Blurred vision	Cataract

GASTROINTESTINAL DISORDERS		
Constipation	Anorexia	Toothache
Diarrhea	Abdominal pain	Gastrointestinal perforation
Nausea	Indigestion	
Vomiting		
GENERAL DISORDERS AND ADMINISTRATION SITE CONDITIONS		
Fatigue	AST increased	Bilirubin increased
Pyrexia	ALT increased	Hepatic failure
Peripheral edema	Asthenia	Tumor lysis syndrome
	Chills	Infusion reaction
	Pain	Allergic reaction
		Multiorgan failure
INFECTIONS AND INFESTATIONS		
	Bronchitis	C-reactive protein increase
Upper respiratory tract infection	Pneumonia	Sepsis
	Urinary tract infection	Febrile neutropenia
		Influenza
METABOLISM AND NUTRITION DISORDERS		
	Decreased appetite	
	Dehydration	
	Hypercalcemia	
	Hyperglycemia	
	Hyperkalemia	
	Hypoalbuminemia	
	Hypokalemia	
	Hypomagnesemia	
	Hyponatremia	
	Hypophosphatemia	
	Hyperuricemia	
	Hypocalcemia	
MUSCULOSKELETAL AND CONNECTIVE TISSURE DISORDERS		
	Chest Pain	
	Arthralgia	
	Back pain	
	Muscle spasms	
	Pain in extremity	
	Myalgia	
	Muscular weakness	
NEOPLASMS BENIGN, MALIGNANT AND UNSPECIFIED		
		Acute myeloid leukemia
		Myelodysplastic syndrome
NERVOUS SYSTEM DISORDERS		
Headache	Dizziness	Posterior Reversible Encephalopathy Syndrome
	Hypoesthesia	
	Insomnia	
	Paresthesia	
	Peripheral neuropathy	

PSYCHIATRIC DISORDERS		
	Anxiety	
	Insomnia	
RENAL AND URINARY DISORDERS		
	Increased creatinine	
	Renal impairment	
	Renal failure	
RESPIRATORY, THORACIC AND MEDIASTINAL DISORDERS		
	Epistaxis	Dysphonia
	Nasopharyngitis	Pulmonary edema
		Pulmonary embolism
Cough		Pulmonary hypertension
Dyspnea		Pulmonary toxicities: Interstitial Lung Disease (including pneumonitis), Acute Respiratory failure and Acute Respiratory Distress Syndrome (ARDS)
SKIN AND SUBCUTANEOUS TISSUE DISORDERS		
	Erythema	
	Rash	
	Pruritis	
	Diaphoresis	

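### The 8% control rate behind the 79% power for cardiovascular toxicity (Section 11.6) does not fit the composite endpoint defined in the same section

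*Combined protocol and SAP*

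**What the plan says.** Section 11.6 (Translational Medicine/Imaging Endpoints) compares between arms the proportion of patients with a clinically relevant cardiovascular toxicity at any time on study. A patient counts with any one of these:

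- heart failure, dyspnea, edema or arrhythmia of CTCAE Grade 2 or higher;
- an LVEF fall of more than 10% from baseline, or to below 53%;
- an increase in global longitudinal strain (GLS) of more than 15%.

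The power statement begins "Assuming a clinically relevant cardiovascular toxicity rate of 8% in the control arm", names "a binomial test with a one-sided significance level of 0.1", and concludes that the design "has 79% power to detect a difference of 15% between arms". No source is given for the 8%.

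Section 2.0 (Background, ECHO) tabulates pooled results from four Phase II carfilzomib studies at 15 to 27 mg/m², introduced by "The cardiac and pulmonary safety profile of carfilzomib in these 4 studies revealed". Of 526 patients, 30 had Grade 3 or higher cardiac failure and 12 had Grade 3 or higher arrhythmia. The row "All grades dyspnea" shows 222 (42%). The adverse event table in Section 3.1c places dyspnea and "Peripheral edema" in its most frequent column, above 20%.

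The comparison serves objective 1.3d, listed under Other Objectives. Section 11.6 closes by calling its analyses exploratory.

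**The concern.** The assumed rate and the endpoint appear to describe different things. Two severe components in the protocol's own low-dose data already come close to 8%, or reach it. The endpoint then adds Grade 2 events, two symptoms listed as common, and two echocardiographic criteria.

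For a fixed absolute difference, a higher control rate (up to roughly 40%) means more binomial variance and less power. What is at stake is how a non-significant result is read. A reader told that a 15-point excess would be missed 21% of the time could take a null finding as reassurance about the higher dose, although the chance of missing it may be appreciably larger.

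**Working it through.** **Inputs.** From Section 11.6: control rate 0.08, difference 0.15 (so 0.23 in the high-dose arm), n = 63 per arm, one-sided alpha 0.1. From Section 2.0: 30, 12 and 222 events among 526 patients.

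**1. Reproducing the 79%.** Normal approximation with continuity correction:

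power = Φ[(d − 1/n − z·SE0) / SE1]

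- SE0 = √(2 × 0.155 × 0.845 / 63) = 0.0645, where 0.155 is the mean of 0.08 and 0.23
- SE1 = √[(0.08 × 0.92 + 0.23 × 0.77) / 63] = 0.0631
- z = 1.2816 and 1/n = 0.0159
- power = Φ[(0.15 − 0.0159 − 0.0826) / 0.0631] = Φ(0.816) = 79.3%

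Full enumeration of Fisher's exact test gives 80.0%. The stated figure is therefore right for its inputs. The uncorrected normal approximation gives 85.7% and does not match.

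**2. Setting the 8% against the background table.**

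- Grade 3 or higher cardiac failure: 30/526 = 5.7%
- Grade 3 or higher arrhythmia: 12/526 = 2.3%
- Either event: 30/526 = 5.7% if all arrhythmia patients also had cardiac failure; 42/526 = 8.0% if no patient had both

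The room left within 8% is 8 − 5.7 = 2.3 points at most, and none at the other extreme. It must hold every patient who qualifies only through Grade 2 heart failure or arrhythmia, Grade 2 or higher dyspnea or edema, or the LVEF and GLS criteria. All-grade dyspnea alone is 222/526 = 42%. Eligibility criterion 5.1m admits patients from an LVEF of 45%, so for someone entering at 45 to 52% even a small fall ends below 53%.

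**3. Changing only the control rate.** Fisher's exact test, 63 per arm, one-sided 0.1. Every rate above 8% is an assumption.

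| Control rate | Power for +15 points | Difference detectable with 79% power |
|---|---|---|
| 8% (plan) | 80% | about 15 points |
| 12% | 74% | about 16 |
| 15% | 71% | about 17 |
| 20% | 66% | about 18 |
| 30% | 62% | about 20 |
| 40% | 57% | about 20.5 |

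The direction does not depend on the test. The uncorrected normal approximation falls from 85.7% at 8% to 73.0% at 20% and 65.9% at 40%.

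**The case against.** **The size of the loss is not in the documents.** This stands. The 42% for dyspnea covers all grades, and the column above 20% for edema gives no grade, whereas the endpoint needs Grade 2 or higher. No LVEF or GLS event rate appears. The four studies mix doses, and the bibliography describes their safety profile as single-agent, while Arm 1 adds dexamethasone. A reader might infer that the true power is 57% to 66%. That holds only if the control rate is assumed to be 20% to 40%; at 12% to 15% the power is 74% to 71%.

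**The 8% need not be exhausted.** This also stands. A reader might infer that severe heart failure and arrhythmia use up the whole 8%, but the table is silent on overlap. The supportable figure is 5.7 to 8.0 points.

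**The effect might scale with the control rate.** Holding the odds ratio implied by 8% versus 23%, (0.23/0.77)/(0.08/0.92) = 3.4, Fisher power would be about 96% to 97% at control rates of 20% to 40%. That is correct arithmetic, but the plan states its effect as an absolute difference of 15%, and its power claim has to be judged on that.

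**The analysis is exploratory and decides nothing.** Largely true. The closing paragraph of Section 11.6 says there are too few patients for meaningful hypothesis testing. Revision 6 added the echocardiography text while accrual was already suspended, and the 63 per arm comes from the PFS calculation in Section 11.2. This limits the weight of the point. It neither justifies the 8% nor withdraws the 79%.

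**Conclusion.** The mismatch is real and minor. The 79% is not a miscalculation; the unsupported element is the 8%, which leaves at most 2.3 points for most of the endpoint it is meant to describe. The power claim is therefore not supported for the composite as defined.

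For a 15-point difference, the chance of missing it rises from the stated 21% to about 26% at a 12% control rate, 34% at 20% and 43% at 40%. This rests on three assumptions: those control rates, the absolute difference kept at 15 points, and the pooled background studies approximating Arm 1. Confidence is high in the inconsistency and moderate at best in the size of the loss.

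A reader might go further and conclude that the trial's design or its safety monitoring is undermined. The documents do not support that: the PFS sample size (Section 11.2) and the toxicity stopping rule (Section 11.7) are calculated separately and do not use this rate.

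**What to change.** In Section 11.6, replace the single 8%/79% statement with one of the following:

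- power for a 15-point difference, or the difference detectable with 79% power, over a range of control rates for the full composite, labelled as assumptions (the table above can serve); or
- no power claim, with the between-arm difference in proportions reported with a confidence interval.

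The existing figures should not be re-attached to a narrower Grade 3 or higher endpoint. That would keep a 23% high-dose alternative, whereas Section 2.0 reports Grade 3 or higher heart failure in 6% of 65 patients at 20/56 mg/m². It would also depart from the Grade 2 endpoint that the section defines.

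Before any composite rate is assumed, the LVEF criterion needs reconciling: Section 11.6 counts a fall of more than 10% or to below 53%, while Section 15.3 describes a fall of more than 10 percentage points to a value below 53%.

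The cost is a sentence or a small table, and a less favourable stated figure. No patients, data or other analyses are affected.
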